### 3.2. Specific Aims & Hypotheses.

Aim 1. Test the effects of CBTw + SE compared to a time and format matched active control of psychoeducation + SE on competitive work outcomes across the 9 month study period. A total of 276 unemployed Veterans with SMI will be randomized to CBTw + SE or the control arm of psychoeducation + SE. Assessed at posttreatment (12 weeks), 6 months (primary endpoint), 9 months and 12 months (to examine sustained effects), the primary outcome will be total weeks worked in competitive jobs. A secondary work outcome, achievement of steady competitive work (i.e. working at least 50% of the follow-up), will be compared between study arms across the 12 month follow up.

Hypothesis 1: Compared to the control arm, participants in the CBTw + SE arm will work significantly more weeks and will be more likely to become steady workers.

Aim 2. Test the effects of CBTw + SE compared to the control arm of psychoeducation + SE on health and recovery at posttreatment (12 weeks), 6 month and 9 month follow up periods. The study will determine the effectiveness of CBTw to improve key health and recovery outcomes including health-related quality of life, suicidal ideation, subjective recovery, symptoms, and mental health service utilization.

Hypothesis 2a: Compared to controls, participants in the CBTw + SE arm will have greater improvement on subjective recovery and health-related quality of life, and decreases in mental health symptoms, suicidal ideation, and inpatient service utilization.

Hypothesis 2b: Greater participation in competitive work will predict improvements in these outcomes over time.

Aim 3. Guided by the RE-AIM implementation framework, conduct an implementation evaluation of CBTw to inform future wide scale roll-out of the intervention across the VHA. Existing Vocational Rehabilitation Counselors (VRCs) at the 3 VA SE programs will deliver CBTw, supported by an initial implementation strategy bundle—site tailored implementation planning, CBTw training, and weekly consultation including audit and feedback. Informed by the RE-AIM implementation framework, data will be collected and utilized to tailor implementation during the study, with assessment of the following RE-AIM domains:

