## **5.1 Study Procedures**

### **5.2 Study Design**

#### **5.2.1 Experimental Design**

WORKWELL is a Hybrid 1 design, two arm RCT with 276 unemployed Veterans who have SMI and are receiving SE services at one of 3 VA sites: Richard L. Roudebush VA Medical Center (RLR), Edward Hines Jr. Hospital (Hines), or the St. Louis VA Health System (St. Louis). Participants will be assigned to one of two study arms: 1) the intervention arm consisting of the 12-week, group-based CBTw plus standard SE services; 2) a time and format matched active control arm consisting of psychoeducation plus standard SE services. The intervention period will last for 12 weeks after which time Veterans will be followed up for an additional 9 months (total of 3 follow-up assessments: posttreatment at 12 weeks, 6 months & 9 months). During the study, participants will receive all standard VA services. The primary outcome will be competitive work (Aim 1) and secondary outcomes of health and recovery will also be evaluated (Aim 2).

SE staff who deliver the CBTw intervention will take part in training led by the study team including education on CBTw content, practice of facilitation strategies, and customization of content to meet Veterans' needs. SE staff who deliver the psychoeducation intervention will take part in training that parallels this structure. Across the study, staff CBTw facilitators will take part in weekly consultation and monthly audit and feedback with study personnel.

Aim 3—Guided by RE-AIM, an evaluation of CBTw implementation will allow for ongoing refinement and finalization of an implementation approach (Aim 3). RE-AIM is an implementation science framework useful for directing the planning and evaluating of interventions, in order to expedite the translation of research into practice. RE-AIM has been successfully utilized across studies, including multiple HSR&D hybrid 1 intervention studies.

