Aim 2: Health and recovery outcomes. Two-level linear regression models accounting for the nested nature of the data (repeated measures nested within individuals) will be used to examine the effects of CBTw + SE services compared to psychoeducation + SE on the change of each of the continuous outcomes including recovery (RAS), health-related quality of life (PCS & MCS), symptoms (DSM), and suicidality (SSI) over time (baseline and 3-, 6-, 9-months follow-ups). It is expected that there will be adequate power (>80%) to detect the treatment effect on health and recovery outcomes even if the effect size is small (i.e., $f^2 = .03$). *Regarding the outcome of suicidal ideation, it is anticipated that the range of responses will be smaller, given that fewer participants will report these thoughts (21.2% of participants in the CBTw open pilot reported passive ideation at baseline; 9.6% reported such thoughts at follow up). Thus, the study may be less powered to detect a treatment effect. However, despite this issue of range restriction given the relatively lower base rate of suicidal thoughts, WORKWELL will nonetheless examine possible treatment effects, due to the importance of this outcome in Veterans with SMI.*

Preliminary analysis: Baseline characteristics of sample & covariates analyses

Given the RCT design, characteristics of participants are expected to be balanced across the two study arms. Baseline characteristics and baseline clinical outcomes (e.g., symptoms) will be compared between the arms using the appropriate test (i.e., t-test, or Chi-square test). Variables found to significantly differ will be included as covariates in the primary analyses. All primary analyses will also include time receiving SE services and site membership as covariates. The potential interaction effects of site with key predictors will also be included as predictors to account for the site effect. Lastly, attendance (the number of CBTw or psychoeducation sessions attended) and the association with the Aim 1 and Aim 2 outcomes will be examined.

Aim 1 Analyses: Competitive Work Outcomes

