Hypothesis 1: For the outcome, total weeks worked in competitive jobs, three-level linear regression models will be used to test the effects of CBTw + SE compared to psychoeducation + SE over time, with predictors of study arm, arm by time interaction, site, and interaction between site and key predictors, covariates, as well as random effects to accommodate the potential non-independence due to repeated measures and group cohort effects. The time effects could be linear or nonlinear; these possibilities will be examined by treating time as continuous or categorical. If the outcomes are not normally distributed, robust maximum likelihood estimation method will be used to correct the standard error estimates for nonnormality. In the case of excess of zeros for this outcome, hurdle negative binomial models, a reliable method to analyze zero inflated longitudinal data of this nature, will be utilized. For the binary outcome, steady competitive work status across the 9-month study period, two-level logistic regression model will be used with the same set of predictors as in the linear models, with random effects to accommodate the potential non-independence due to group cohort effects.

Aim 2 Analyses: Health and Recovery Outcomes

To test **Hypothesis 2a**, Two-level linear regression models accounting for the nested nature of the data (repeated measures nested within individuals) will be used to examine the effects of CBTw + SE services compared to psychoeducation + SE on the change of each of the continuous outcomes including recovery (RAS), health-related quality of life (PCS & MCS), symptoms (DSM), and suicidality (SSI) over time (baseline and 3-, 6-, 9-months follow-ups). The scores of the outcome measures are calculated by averaging the corresponding items. The models are the same as those in Aim 1 analysis except that the outcomes are different. It is hypothesized that CBTw + SE will lead to a greater improvement on the health and recovery outcomes (indicated by a significant arm by time effect). If the outcomes are not normally distributed, robust maximum likelihood estimation method will be used to correct the standard error estimates for nonnormality.

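### Hypothesis 2a is judged by an arm-by-time effect with a free arm difference at the randomised baseline; this wastes power on every trajectory examined and, with linear time, counts the 12-week benefit negatively.

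*SAP*

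**What the plan says.** The SAP, under Aim 2 Analyses, models each continuous health and recovery outcome "over time (baseline and 3-, 6-, 9-months follow-ups"), so baseline is one of four outcome visits. It gives one criterion for Hypothesis 2a: "CBTw + SE will lead to a greater improvement on the health and recovery outcomes (indicated by a significant arm by time effect").

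The model comes from Aim 1: "The models are the same as those in Aim 1 analysis except that the outcomes are different". The Aim 1 predictors include study arm and its interaction with time, so the arm difference at baseline is a free parameter. On the form of time, the Aim 1 text says: "The time effects could be linear or nonlinear; these possibilities will be examined by treating time as continuous or categorical". It gives no rule for choosing.

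Protocol 3.2 frames Aim 2 as the effect of CBTw "on health and recovery at posttreatment (12 weeks), 6 month and 9 month follow up periods". Protocol 5.6 (Study Evaluations) says the arms will be compared on these outcomes at every assessment. Protocol 5.2.1 puts the end of treatment at the first follow-up visit: "The intervention period will last for 12 weeks".

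On power, the SAP writes "It is expected that there will be adequate power (>80%) to detect the treatment effect on health and recovery outcomes even if the effect size", and puts that effect at f² = .03, which it calls small. It gives no standard deviation, correlation or time pattern for these outcomes.

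**The concern.** The question in the protocol is whether CBTw participants are better off than controls at 12 weeks, 6 months and 9 months. The SAP's criterion answers a different question, in two respects.

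- **Baseline.** Randomisation gives the arms one expected baseline mean. A model with a free baseline arm difference estimates something known to be zero, and every interaction estimate carries that extra variance.
- **Shape.** With continuous time the criterion tests equal straight-line slopes. A difference that is present at week 12 and then stays level is not a difference in straight-line growth, and the test detects it poorly. With categorical time, if the criterion is read as the joint interaction test, it becomes a three-degree-of-freedom test with no direction.

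CBTw could improve recovery or symptoms at every follow-up visit and still be reported as not supporting Hypothesis 2a. Because the form of time is open, that verdict could also turn on a choice made after the data are seen.

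**Working it through.** **The plan's own figure.** The Aim 2 power is a lower bound whose settings are not given, so it cannot be uniquely reproduced. With one observation per person, f² = .03 gives 81.8% power at N = 276 and 76.2% at N = 240. With four measures at ICC .2 and N = 240, the effective N is 240 × 4/(1 + 3 × .2) = 600 and power is 98.8%. Dividing further by a cohort design effect of 1 + 7 × .077 gives 92.6%. More than 80% is plausible, but the figure assumes no particular trajectory.

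**Inputs.** From the documents: 138 per arm, 13% attrition (276 × .87 ≈ 240, so n = 120 per arm), α = .05, visits at 0, 3, 6 and 9 months. Assumed: two-sided test, equal visit SDs of 1, compound symmetry with ρ = .2, .5, .7. Only .2 is in the SAP, and it is given for weeks worked. No cohort clustering is included, as the SAP writes the Aim 2 model as two-level. Normal approximation; z(.975) + z(.80) = 2.802.

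**Step 1: slope weights.** With a free arm term and equally spaced visits, the weights on the four arm differences are −3, −1, +1, +3. The 12-week difference enters negatively. For a flat effect (0, d, d, d) the contrast is −d + d + 3d = 3d, with variance (2/n) × 20(1 − ρ).

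**Step 2: reference effect.** The baseline-adjusted mean of the three follow-up differences has variance (2/n)[(1 + 2ρ)/3 − ρ²]. For ρ = .2 the bracket is .4667 − .04 = .4267. For 80% power, d = 2.802 × √(.4267/60) = .236 SD.

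**Step 3: planned linear test, flat effect.** At ρ = .2 the noncentrality is 3 × .236/√(20 × .8/60) = 1.37, and power is 28%. The same steps give 40% at ρ = .5 and 48% at ρ = .7. A Monte Carlo check with 6,000 replicates gave 27.9%, 39.8% and 47.6%.

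**Step 4: joint categorical test.** The noncentrality is (n/2) Σ(dⱼ − d̄)²/(1 − ρ) on 3 df. For the flat effect the sum is .75d², and power is 29%, 43% and 52%.

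**Step 5: other comparators, flat effect.**
- Unadjusted mean change has variance (2/n)(4/3)(1 − ρ). Set at 80%, it leaves the linear test a noncentrality of 2.802 × 3 × √((4/3)/20) = 2.17, or 58%: a loss of about 22 points at any ρ.
- Change to 9 months has variance (2/n) × 2(1 − ρ). The noncentrality is 2.802 × 3 × √(2/20) = 2.66, or 76%: a loss of about 4 points.
- A single baseline-adjusted visit: a loss of 26 to 11 points for ρ = .2 to .7.

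**Step 6: constrain the baseline, keep linear time.** The slope is now fitted through zero at baseline. With t = (0, 1, 2, 3) and c = ρ/(1 + 3ρ), the noncentrality is √(60/(1 − ρ)) × (t·d − 6cΣdⱼ)/√(14 − 36c). At ρ = .2, c = .125. For the flat effect this is 8.66 × (6 − 2.25) × .236/√9.5 = 2.49, or 70%.

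Power (%), each effect sized for 80% on the baseline-adjusted follow-up mean:

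| Arm-difference shape | Planned linear, ρ = .2 | Baseline constrained, ρ = .2 | Planned linear, ρ = .7 | Baseline constrained, ρ = .7 |
|---|---|---|---|---|
| Flat (0, 1, 1, 1) | 28 | 70 | 48 | 62 |
| Fading (0, 1, .75, .5) | 12 | 53 | 19 | 32 |
| Faster fade (0, 1, .5, .25) | 5 | 37 | 6 | 12 |
| Linear growth (0, 1, 2, 3) | 63 | 88 | 89 | 93 |
| Delayed (0, 0, .5, 1) | 89 | 97 | 99.4 | 99.6 |

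The constraint helps in every row. It does not cure the weighting alone: the 12-week weight is proportional to 1 − 6c, which is +.25 at ρ = .2 but −.35 at ρ = .7.

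**Step 7: what an averaged contrast gives up.** Size the delayed effect so that the planned linear test has 80%. The baseline-adjusted average then has 69%, 50% and 42% at ρ = .2, .5 and .7, a loss of 11 to 38 points.

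**The case against.** The strongest reply is that an arm-by-time test suits the benefit this plan may expect. Protocol 5.6 sets the work endpoint at 6 months so that skills can be practised and consolidated. Hypothesis 2b links health gains to competitive work, which accumulates from zero in people unemployed at baseline. A delayed benefit is therefore plausible, and for it the linear test (89% to 99%) beats the averaged contrast (80%). This stands. A reader might infer that a gain by week 12 that then holds or fades is the likeliest course for a 12-week treatment; no passage says so.

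Second, linear time is only one of two permitted forms. With categorical time each arm-by-visit coefficient is a signed difference in change from baseline, the SAP never names the joint test, and the protocol compares arms at every visit. This also stands, and an early benefit need not go unseen. But the criterion for supporting Hypothesis 2a remains an interaction of unspecified form, and the free baseline difference is present in both forms.

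Third, the size depends on assumptions. Adding the SAP's cohort ICC of .077 as a constant cohort intercept (8 per group, total ρ = .2) raises the 28% to 39.6%. First-order autoregressive correlation works the other way: the loss against the baseline-adjusted mean becomes about 41 to 57 points.

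It might also be said that the plan already adjusts for baseline. The SAP's Preliminary analysis adds baseline variables only if they differ significantly between arms, and routine control for baseline levels appears only under Hypothesis 2b. Neither supplies it for Hypothesis 2a.

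**Conclusion.** The concern holds in a limited form. The Hypothesis 2a model ignores the shared randomised baseline, and correcting that raised power for every trajectory examined. With linear time the criterion also gives the 12-week difference a negative weight and detects an early, sustained or fading benefit poorly: 28% to 48% power for a flat effect, where the baseline-adjusted follow-up mean has 80%. That range rests on compound symmetry with ρ from .2 to .7, 120 per arm and no clustering.

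Three stronger readings are not supported.

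- A reader might take the gap of 32 to 52 points (80 − 48 and 80 − 28) as a property of the plan. It belongs to one comparator and one shape; across the compound-symmetry comparators the loss runs from about 4 to 52 points.
- A reader might conclude that the stated power above 80% requires straight-line growth. The SAP gives no trajectory from which to derive that.
- A reader might think an averaged contrast costs at most about 9 points, as it does for linear growth at ρ = .7 (89% against 80%). For a delayed benefit it costs more.

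These are secondary outcomes, and the issue is power and an unfixed contrast. No bias or inflated type I error has been shown for either form of the test taken alone.

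**What to change.** In the SAP's Hypothesis 2a text:

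1. Constrain the baseline mean to be equal across arms, or use baseline as a covariate with only the three follow-up visits as outcomes.
2. Use categorical time, and report the baseline-adjusted arm difference with a 95% confidence interval at 12 weeks, 6 months and 9 months, to match the protocol.
3. Name one contrast that decides Hypothesis 2a for each outcome, before any Aim 2 results by arm are seen. The averaged follow-up difference is a reasonable choice for improvement at follow-up. If the investigators expect a delayed benefit, they should weigh the 11 to 38 points it can give up.
4. Keep arm-by-time as a description of trajectory, and restate Aim 2 power for the named contrast with its assumed correlation and time pattern.

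The cost is SAP wording and a power recalculation. No visit, measure or sample size changes. The baseline change lost power for none of the shapes examined; the choice of contrast is a real trade-off between early and late benefit.

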#### *Health and Recovery Outcomes (Hypotheses 2a & 2b)*

To test **Hypothesis 2a**, three-level linear regression models (i.e. mixed models) accounting for the nested nature of the data will be used to test the effects of CBTw + SE services compared to psychoeducation + SE on each of the continuous outcomes including recovery (RAS), health-related quality of life (PCS & MCS), symptoms (CCSM), and suicidality (SSI) over time. For the count outcome of service utilization, three level Poisson regressions will be used to examine group differences over time on number of days of inpatient hospitalization. If there is a problem of excess of zeros for utilization (e.g., no hospitalizations), hurdle negative binomial models will be used.

To test **Hypothesis 2b**, three-level linear regression models will examine the effects of work on health and recovery outcomes over time, with predictors of competitive weeks worked, time, weeks by time interaction, site membership and potential interaction between site and key predictors, potential covariates (i.e. controlling for baseline levels of health and recovery), as well as random effects to accommodate the potential non-independence due to repeated measures and group cohort effects.

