To test **Hypothesis 2b**, two-level linear regression models will examine the effects of work on health and recovery outcomes over time, with predictors of competitive weeks worked, time, weeks by time interaction, site membership and potential interaction between site and key predictors, potential covariates (i.e. controlling for baseline levels of health and recovery), as well as random effects to accommodate the potential non-independence due to repeated measures and group cohort effects.

Missing data: Aims 1 & 2

Missing data from Aims 1 and 2 will come in two different forms: missing by attrition and intermittent missing of observation. Using logistic regression, the effects of missing observations due to sample attrition will be examined by investigating the participant characteristics associated with dropout. If results reveal that data are missing completely at random (MCAR) or due to observed factors (MAR), the data will be analyzed using full information maximum likelihood, taking into account potential predictors for missingness. However, if the pattern of missing data is nonignorable, pattern-mixture models that includes variables defined by the participant's pattern of missing data will be used. Sensitivity analyses also will be performed to examine how the result will change based on different assumptions about the missing data, such as the missing work period having no work, the mean amount of work as available data from earlier follow-up periods, or full employment.

Account for Heterogeneity in the Sample

The study is limited to working aged Veterans with SMI who are unemployed at baseline, decreasing the heterogeneity of the sample. In addition, analyses will examine whether treatment effect will change as a function of the site membership and major characteristics of the study participants, such as different types of SMI diagnoses, age, and current substance use (e.g., users vs. non-users).

AIM 3 CBTw IMPLEMENTATION: OVERVIEW

The initial CBTw implementation strategy was informed by implementation science and developed based on our experience in the two CBTw pilots, stakeholder surveys and interviews, and feedback from operational partners. *In order to ensure successful implementation of CBTw during WORKWELL and wide-scale uptake following its completion, an evaluation of this initial implementation strategy and barriers and facilitators of implementation will be conducted, guided by the RE-AIM framework.*

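### The Hypothesis 2b model omits study arm, so a direct effect of CBTw on health may be reported as an effect of work

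*SAP*

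**What the plan says.** Protocol 3.2 words the hypothesis as a prediction: "Greater participation in competitive work will predict improvements in these outcomes over time". The analysis sections go further. In the SAP (Aim 2 Analyses, Hypothesis 2b), "two-level linear regression models will examine the effects of work on health and recovery outcomes over time". The Protocol (5.6 Data Analysis, Health and Recovery Outcomes) has the same sentence with one more level: "three-level linear regression models will examine the effects of work on health and recovery outcomes over time".

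Both documents give the same model:

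- **Fixed effects:** "with predictors of competitive weeks worked, time, weeks by time interaction, site membership and potential interaction between site and key predictors".
- **Covariates:** "potential covariates (i.e. controlling for baseline levels of health and recovery"). Nothing else is named.
- **Random effects:** "as well as random effects to accommodate the potential non-independence due to repeated measures and group cohort effects".

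The Hypothesis 1 model is specified "with predictors of study arm, arm by time interaction, site, and interaction between site and key predictors, covariates", and the SAP carries that model over to Hypothesis 2a. The general covariate rule (SAP, Preliminary analysis; same text in Protocol 5.6) adds time in SE, site and any baseline variable that differs between arms. It does not add arm. Weeks worked enters Hypothesis 2b as a single term.

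**The concern.** Participants are not randomised to weeks worked. The intervention is meant to change it. Hypothesis 2a expects CBTw to improve recovery, quality of life, symptoms and suicidal ideation. Hypothesis 2a does not say by which route, but the Protocol Introduction argues that CBT approaches improve health in their own right. If part of the benefit does not pass through work, arm is a common cause of exposure and outcome. Leaving it out then biases the weeks coefficient towards a benefit of work.

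A second source of confounding is personal. The Introduction links motivation, hope, self-esteem and self-efficacy to work outcomes, and such traits could also drive recovery scores. A single weeks term cannot separate people who work more from periods in which a person works more.

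At stake is what the trial may say about work as a cause of better health, an idea that is in its title.

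**Working it through.** **No stated figure to reproduce.** Neither document gives power or an error rate for Hypothesis 2b. As a calibration on the nearest figure (SAP: 97.6% power for the Aim 1 arm-by-time effect at f² = .03):

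- Completers: 276 × 0.87 = 240.
- λ = .03 × 240 × 3 / (1 + 2 × .2) = 21.6 / 1.4 = 15.43, and √λ = 3.93.
- Power = Φ(3.93 − 1.96) = 97.5%.

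This agrees, but other variants also come close, so it does not identify the SAP's own simulation.

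**Inputs for the check.** From the SAP: planning effect f² = .03 on weeks and on health, pilot f² = .15 on weeks, cohort ICC .077, repeated-measures ICC .2, α = .05. From Protocol 5.2.2: cohorts of up to 8. Assumed: a two-sided test, a true work effect of zero (so any CBTw effect on health is direct), and f² read as a between-arm effect with d = 2√f². That gives d = .35 for f² = .03 and d = .77 for f² = .15.

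**Hand calculation (one time point, no baseline adjustment, no clustering).** If arm is the only link between weeks and health, their spurious correlation is the product of their correlations with arm:

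r = √[f²w/(1+f²w) × f²h/(1+f²h)], z = r√240, rejection = Φ(−1.96+z) + Φ(−1.96−z).

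| f² on weeks | f² on health | r | z | rejection |
|---|---|---|---|---|
| .03 | .03 | .029 | 0.45 | 7.4% |
| .11 | .03 | .054 | 0.83 | 13.2% |
| .15 | .03 | .062 | 0.95 | 15.9% |

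**Simulation of the listed model.** The main set-up had 240 completers in 30 cohorts of 8 and follow-up at 3, 6 and 9 months. Cumulative weeks came from a weekly job-start and job-loss process, with 500 to 1,500 replications. Rejection means a joint 5% test of weeks and weeks by time. Simpler set-ups with 240 people and three follow-ups supplied the rows at the full pilot value. Monte Carlo standard error near 5% is √(.05 × .95/1500) = 0.6 points at 1,500 replications and 1.0 point at 500.

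| Scenario, true work effect zero, d = .35 on health | No cohort term | With cohort random effect |
|---|---|---|
| No confounding | 5% | – |
| Planning-size effect on weeks | 6–8% | 5–6% |
| Effect on weeks f² about .11 | 11–12% | 6–7% |
| Effect on weeks at pilot size | 14–20% | 7–12% |

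**Does adding arm cure it?** Arm alone still left 9–14% where the health effect grows over follow-up and the effect on weeks is large. Arm with arm by time brought rejection to about 4–6%. Both terms are needed, because Hypothesis 2a itself expects an arm-by-time effect.

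**Person-level confounding (strengths assumed, not in the documents).** With a latent trait that affects both job starts and health, the listed two-level model rejected in these shares of trials:

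| Assumed trait | As listed | Plus arm and arm by time | Within-person term after the split |
|---|---|---|---|
| Stable, moderate | 13% | 12% | 5% |
| Recovery slope, moderate | 16% | 17% | 6% |
| Both traits plus arm effect | 52% | 39% | 6% |
| Recovery slope, strong | 94% | 95% | 7% |

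These rows show direction and sensitivity only. The spread reflects what was assumed about the trait.

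**The case against.** **The cohort random effect.** Cohorts are nested within arm, so a cohort random effect absorbs part of the omitted arm effect. At the planning effect size it leaves almost no inflation (5–6%). This stands for the Protocol's three-level model. It is less secure under the SAP, which calls the model two-level while also asking for cohort effects.

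**The pilot value.** f² = .15 comes from an open trial with no control group. Reading it as a between-arm difference against an active control is an assumption, so the upper range is conditional.

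**The hypothesis is predictive.** Protocol 3.2 says that work will predict improvement, and the data-collection text in 5.6 speaks only of a relationship. A reader might infer that only within-person change can answer Hypothesis 2b, so that a between-person finding is a false positive. The documents do not support that. With baseline health and weeks by time in the model, a finding that people who work more improve more is a legitimate answer to the hypothesis as worded. The overreach is in the analysis sections, which describe the estimate as what work does to health. Whether the within-person term should be primary is a choice on which statisticians may differ.

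**Certainty.** A reader might also infer that a direct CBTw effect, or a trait such as motivation, is bound to surface as a work effect. It may do so. How often depends on effect sizes and trait strengths, and the documents do not give the trait strengths.

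**Conclusion.** The omission is real, and nothing elsewhere in either document supplies arm for Hypothesis 2b. Without a cohort term, the false-positive rate for a work effect is about 6–8% at the SAP's planning effect and about 11–20% if CBTw changes weeks worked by an amount near the pilot value. A cohort random effect brings these to about 5–6% and 6–12%. The figures assume that the CBTw effect on health is f² = .03 and wholly direct, and that nothing else links work and health. Person-level confounding could be larger than the arm problem, and adding arm does not remove it, but no figure for it can be drawn from the documents.

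This is a modest and easily corrected fault in a secondary, observational analysis. It would be wrong to infer that the trial's main results are compromised: the randomised comparisons under Hypotheses 1 and 2a do not depend on this model.

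**What to change.** In the Hypothesis 2b paragraphs of the SAP and Protocol 5.6:

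1. Add study arm and arm by time to the predictors. Arm alone is not enough. Arm precedes work, so adjusting for it does not remove any true effect of work.
2. Describe the weeks-worked coefficient as an association and drop the effect wording.
3. As a supporting analysis, enter weeks worked as two terms: the person's mean, and the deviation from that mean in the interval before each assessment. State that the within-person term is still open to reverse causation (better health leading to work) and to time-varying confounding.

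In the same edit, state whether weeks are cumulative or per interval, and settle whether the model has two or three levels, since the cohort term affects the bias.

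**Cost.** SAP and protocol wording and two or more extra terms. Work is already recorded monthly, so no new data are needed. Intervals widen slightly: in the single-time-point approximation, adding arm multiplies the standard error for weeks by √(1 + f²w), which is √1.03 = 1.015 at the planning effect and √1.15 = 1.07 at the pilot value. The within-person term will be less precise.
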